29 a "morselized, flowable tissue allograft derived from amniotic tissues. Amniotic tissues have been shown
30 to support soft tissue repair, reduce inflammation and minimize scar tissue formation".^{6,7}

31

32 This study will compare corticosteroid injection to BioDRestore injection in patients with significant
33 (Kellgren-Lawrence grade 3-4) knee osteoarthritis. Our hypothesis is that BioDRestore will result in
34 better outcomes than corticosteroid when injected intra-articularly in patients with knee OA.

35

36 **2. Study Endpoints**

37

38 Primary Endpoint

- 39 • Visual Analog Score (VAS), VR-12, Lysholm, SANE and Knee Injury and Osteoarthritis
40 Outcome Score (KOOS) at the 6-week, 3-month, 6-month, and 12-month post-injection time
41 periods.

42

43 Secondary Endpoints

- 44 • Inflammatory markers at 6-months post-injection.

45

46 **3. Subject Recruitment and Screening**

47

48 *Screening*

49 Patients who present with osteoarthritis of the knee and are recommended for a knee
50 injection will be screened for inclusion into the study. Following discussion of the
51 study between the patient and the treating physician, the patient will be given the
52 opportunity to move forward with the informed consent process.

53

54 *Enrollment*

55 The subject will be considered enrolled once voluntary informed consent has been
56 given, and the form has been signed and dated by all required parties.

57

58 *Randomization*

59 Subjects will be randomized to a treatment arm (corticosteroid or BioDRestore injection)
60 using a 1:1 ratio. Once study eligibility has been confirmed, the study coordinator or
61 designee will randomize the subject to a treatment arm. The treatment for each subject
62 will be assigned through the study database.

63
64
65
66
67
68
69
70
71
72
73
74
75
76
77
78
79
80
81
82
83
84
85
86
87
88
89
90
91
92
93
94
95
96
97
98
99
100
101
102
103
104
105
106
107
108
109
110
111
112

Blinding

Study subjects and investigators will be blinded to the treatment assignment for the duration of the study to reduce the risk of bias. The research coordinator will provide the randomization to the investigator’s medical assistant (MA) prior to treatment in order for the MA to assist with preparation of the injection.

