- Patient Outcomes: Subject to complete VAS, VR-12, KOOS, Lysholm and SANE prior to injection.
- Range of Motion Assessment: Measurement taken using goniometer.

Visit 2- Randomization & Procedure

- **Inclusion/Exclusion review**
- **Randomization**
- Procedure: For patients with current knee effusion, the investigator will drain the effusion prior to the injection. For subjects that do not exhibit any signs of knee effusion, the investigator will proceed with the injection. Study subjects will be randomized to receive a cortisone or BioDRestore injection. Subjects will be blinded to the assignment. Prior to the injection, the area will be prepared with sterile solution and numbing agent. Next, an injection of one of the following treatments, dependent on randomization, will be injected into the articular space of the knee:

_2 cc of 40 mg/ml Kenalog with 3 cc of saline

_2 cc BioDRestore with 3 cc of saline

Knee arthrocentesis (for procedure, see below under "Follow-up Visits"): The study doctor will attempt to perform a knee aspiration to provide a delta value for the assay.

Follow-Up Visits (6WK, 3M, 6M, 12M)

The following information will be collected at each follow-up visit:

- 162 • Patient Outcomes: Subject to complete VAS, VR-12, KOOS, Lysholm, and SANE scales
163 • **6-month only, subject will return to the clinic for the following:**
164 ▪ Range of motion assessment
165 ▪ Knee arthrocentesis (aspiration): The area will first be prepared with sterile
166 solution and numbing agent. Using a 10-mL syringe, obtain at least
167 0.25mL of synovial fluid via a parapatellar approach. A knee aspiration
168 attempt will be made on all subjects that produced an adequate sample at
169 baseline prior to the injection. Upon completion, the syringe will be
170 labeled and transported to the Clemson Bioengineering Laboratory of
171 Orthopaedic Tissue Regeneration & Orthobiologics lab for analysis.
172 ▪ Aspirate analysis: Enzyme linked immunosorbent assay (ELISA) will be
173 performed on synovial fluid aspirated from the knees of study patients at 6
174 months post-injection to determine if there are quantitative differences in
175 soluble mediators and products of osteoarthritis. Briefly, synovial fluid
176 samples will be evaluated in duplicate for inflammatory (interleukin-1 beta;
177 IL-1 β and tumor necrosis factor-alpha; TNF- α), anti-inflammatory
178 (interleukin-1 receptor agonist; IL-1RA and interleukin-10; IL-10), pain

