336 concerning the effect per FDA and/or IRB requests.
337

338 339 **9. Source Documentation**

340 Investigators are responsible for obtaining and maintaining complete subject health information in the
341 medical record for each subject and each assessment in the protocol (source documents). Source
342 documents include all information in original records and certified copies of original records of clinic
343 findings, observations or other activities in the study necessary for the reconstruction and evaluation
344 of the trial. Source data are contained in source documents (e.g., hospital records, clinic and office
345 charts, memoranda, dispensing records, subject questionnaires, clinic evaluation transcriptions,
346 operative notes, x-rays, radiology reports, blood collection and shipment records, research subject
347 files, etc.)
348

349 **10. Disclosure of Data and Data Security**

350 351 *Data Security and Confidentiality*

352 The clinical data obtained in this study will be kept private. In any sort of published
353 report, there will be no identifying information. Records for this study may be reviewed

354 by the IRB and/or other government agencies may inspect and photocopy all medical
355 records applicable to involvement in this study.
356

357 Participating subjects will be asked to sign a consent form that includes an authorization
358 to use and/or disclose personal health information. Subjects are free to refuse
359 authorization to transfer personal information. If the subject chooses not to agree to this
360 authorization, the subject is not eligible to participate in the study. Personal information
361 (including sensitive personal health information, such as medical history) if relevant to
362 the study will be reviewed, collected in a computer database, stored in electronic or
363 manual files, audited, and / or otherwise processed by the investigator, regulatory
364 agencies, and other persons and/or agencies as required by law or allowed by applicable
365 regulations.

366 **11. Statistical Procedures**

367 **11.1 Sample Size Estimate**

368
369 To determine sample size, we powered the study (a-priori) for the primary outcome measures of VAS,
370 VR-12, KOOS, Lysholm, and SANE scales at baseline, 6-week, 3-month, 6-month, and 12-month post-
371 injection time periods. Assuming normal distributions among the 2 independent groups' 5 time-points for

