372 2 groups and five outcome measures, and assuming an effect size of 0.20 (small) based on between group
373 differences we constructed a sample size estimation using a Multivariate Analysis of Variance
374 (MANOVA). Measuring global effects, with an expected 80% power, and a standard error of probability
375 of 0.05, we estimate the need for a minimum sample size of 70 for statistical significance (~35 per group).
376 To account for a 20% drop-out rate, a sample size of 84 subjects will be recruited. We will employ
377 intention to treat and a chains equation, multiple imputation method in which we will assign predictor,
378 structural and impute variables. Further, we will not oversample characteristics within each group for
379 drop-outs.
380
381

382 **11.2 Data Analyses**

383
384 Descriptive statistics will be used to describe both groups at baseline. Appropriate tests of differences will
385 be used to compare baseline differences in descriptive statistics, pain, range of motion, etc., between the
386 two groups (e.g., t-tests and chi-square). Adverse events, including severity of these events will be
387 captured and compared between the two groups. A Multivariate Analysis of Variance (MANOVA) will
388 be used to measure differences between the targeted outcome measure at each of the given timepoints
389 (baseline, 6-week, 3-month, 6-month, and 12-months post-injection time periods). A MANOVA
390 investigates the effects of a categorical predictive variable (groups) on 2 or more continuous outcomes,
391 which are correlated and represented by a vector of dependent variables. For all analyses, a p value of
392 <0.05 will be considered statistically significant.
393
394
395
396
397

398 **12. Bibliography**

- 399 1. Divine J, Zazulak B, Hewett TE. Viscosupplementation for knee osteoarthritis. Clin Orthop Rel
400 Res. 2006; 455:113-122.
- 401 2. Dawson J, Linsell L, Zondervan K, et al. Epidemiology of hop and knee pain and its impact on
402 overall health status in older adults. Rheumatology. 2004; 43:497-504.
403

404 3. Laupattarakasem W, Laopaiboon M, Laupattarakasem P, Sumananont C. Arthroscopic
405 debridement for knee osteoarthritis (Review). Cochrane Collaboration. Issue 4, 2009.
406 4. Younes M, et al. Systemic effects of epidural and intra-articular glucocorticoid injections in
407 diabetic and non-diabetic patients. *Joint Bone Spine*. 2007, 74(5): 472-6.

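### Baseline is listed as a tested MANOVA timepoint and never used as a covariate; prespecifying baseline adjustment is a cheap precision gain, not the repair of an error

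*Combined protocol and SAP*

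**What the plan says.** Section 11.2 states that a MANOVA will "be used to measure differences between the targeted outcome measure at each of the given timepoints", and lists those timepoints as "baseline, 6-week, 3-month, 6-month, and 12-months post-injection time periods". Group is the only predictor it names. The outcomes are described as ones "which are correlated and represented by a vector of dependent variables", but the make-up of that vector is not given. Section 11.1 uses the same list for the sample size: "VR-12, KOOS, Lysholm, and SANE scales at baseline, 6-week, 3-month, 6-month, and 12-month post"-injection.

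Section 2 defines the primary endpoint on the post-injection visits only: "Outcome Score (KOOS) at the 6-week, 3-month, 6-month, and 12-month post-injection time" periods. Under Visit 1, section 5 has all five scales recorded before treatment: "Patient Outcomes: Subject to complete VAS, VR-12, KOOS, Lysholm and SANE prior to injection".

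Section 11.2 also plans separate tests to "be used to compare baseline differences in descriptive statistics, pain, range of motion, etc., between the" two groups. No covariate, change score or time interaction appears anywhere. The predictor variables mentioned in section 11.1 belong to the multiple imputation, not to the analysis model.

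**The concern.** Baseline is placed where it cannot show a treatment effect, and left out where it could help. What this costs depends on how the response vector is read.

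- **Five scales at one visit.** This is suggested by testing at each timepoint. One of the five MANOVAs then tests a baseline difference that randomization makes null, and that is tested separately anyway. The other four ignore the baseline scores.
- **One scale over five timepoints.** This is allowed by the singular outcome measure and the reference to a vector. Baseline then sits among the responses. It recovers most of the precision by that route, but spends a response dimension on a component with no treatment effect.

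Type I error is not at stake on either reading. At stake are power and the reported estimates: a chance difference at baseline passes in part into the follow-up difference and is not corrected.

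**Working it through.** **Inputs from the documents.** Two arms, 1:1; five outcome measures; effect size 0.20; alpha 0.05; power 80%; 70 evaluable subjects (about 35 per group); 84 recruited (42 per arm), analysed by intention to treat with multiple imputation.

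**Assumed.** The baseline-to-follow-up correlation r, taken from 0 to 0.7.

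**Step 1: the plan's own figure.** Take 0.20 as the MANOVA f², with p = 5 responses and two groups. The global test is F with df1 = 5, df2 = N − 6 and noncentrality λ = 0.20 × N.

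- N = 70: df2 = 64, λ = 14.0, power 0.801.
- N = 69: power 0.794.
- N = 84: df2 = 78, λ = 16.8, power 0.882. This is an upper bound that assumes no information is lost to drop-out.

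So the stated 70 reproduces exactly without a covariate. The sample size takes no credit for baseline data.

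**Step 2: five scales at one visit, adjusted for the five baselines (MANCOVA).** Residual variance shrinks by 1 − r². Five error degrees of freedom go, and chance imbalance costs roughly a factor (N − 5)/N. Hence df2 = N − 11 and λ = 0.20 × (N − 5)/(1 − r²).

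| r | λ, N = 70 | Power, N = 70 | λ, N = 84 | Power, N = 84 |
|---|---|---|---|---|
| unadjusted | 14.0 | 0.801 | 16.8 | 0.882 |
| 0 | 13.0 | 0.762 | 15.8 | 0.857 |
| 0.3 | 14.3 | 0.807 | 17.4 | 0.892 |
| 0.5 | 17.3 | 0.886 | 21.1 | 0.947 |
| 0.7 | 25.5 | 0.977 | 31.0 | 0.994 |

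Break-even is at r of about 0.28 (N = 70) and 0.25 (N = 84). If r falls over the four visits as 0.5, 0.4, 0.3, 0.2, adjusted power at N = 70 is 0.89, 0.84, 0.81 and 0.78; the 12-month test then loses about 2 points.

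Simulation at N = 70 (3,000 trials per r, inter-scale correlation 0.5) gave adjusted power of 0.76, 0.80, 0.89 and 0.98 at r = 0, 0.3, 0.5 and 0.7. Null rejection was 0.044 to 0.058 over both tests, so both are valid.

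**Step 3: one scale over visits.** Further assumptions: a 0.6 SD effect at every post-injection visit, correlation 0.6 between follow-up visits, and r no larger than that. With n per arm, conditioning on baseline gives λ = (n/2) × 4 × 0.36/(2.8 − 4r²). At n = 35 this is 25.2/(2.8 − 4r²) = 9.0, 10.3, 14.0 and 18.5 at r = 0, 0.3, 0.5 and 0.6.

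- Baseline in the vector: df 5 and 64, λ as above.
- Own baseline as covariate: df 4 and 64, λ × 67/68 for chance imbalance.

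| r | In vector, 35 per arm | Covariate, 35 per arm | In vector, 42 per arm | Covariate, 42 per arm |
|---|---|---|---|---|
| 0 | 0.581 | 0.619 | 0.681 | 0.718 |
| 0.3 | 0.650 | 0.688 | 0.750 | 0.784 |
| 0.5 | 0.801 | 0.831 | 0.882 | 0.904 |
| 0.6 | 0.910 | 0.928 | 0.959 | 0.969 |

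The gain is 2 to 4 points at 35 per arm and 1 to 4 at 42. The four visits alone, with no baseline at all, give 0.627 at 35 per arm. At r = 0 the single covariate therefore costs under 1 point (0.627 to 0.619).

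**Step 4: chance imbalance at 42 per arm.** The standard error of a baseline mean difference is √(2/42) = 0.218 SD. The chance that a given scale differs by more than 0.25 SD is 2 × [1 − Φ(0.25/0.218)] = 0.25. An unadjusted follow-up difference carries about r times a 0.25 SD gap:

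- r = 0.3: 0.075 SD, or 0.34 of its own standard error.
- r = 0.5: 0.125 SD, or 0.57.
- r = 0.7: 0.175 SD, or 0.80.

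**The case against.** **No defect is shown.** The unadjusted tests hold their level, and the planned 70 delivers 80% power without adjustment. This stands, and the point is offered as an improvement only.

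**The gain rests on quantities the documents do not give.** It is small if the vector is one scale over visits, and with five covariates it is negative when r is low. This also stands; the loss is at most about 4 points at N = 70.

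**r alone does not settle the gain.** Step 2 assumes that each cross-scale baseline-to-follow-up correlation equals r times the inter-scale correlation. Take N = 70, inter-scale correlation 0.5 and own-scale r = 0.5, and raise the cross-scale value from 0.25 to 0.40. Adjusted power is then 0.798 if the effect falls on one scale only, against 0.801 unadjusted, but 0.977 if all scales benefit equally. The break-even values are therefore approximate. The argument cuts both ways and does not favour leaving baseline out.

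**Imbalance is not bias over repeated randomizations.** Correct: the unadjusted standard error already allows for it, and the 0.25 SD threshold is illustrative. The estimate from this one trial is nevertheless left uncorrected.

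**Parts of the remedy are reporting style or already possible under the plan.** Dropping baseline significance tests is a matter of reporting, and nothing in section 11.1 excludes baseline scores from the imputation model. Neither remark touches the core change.

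**Conclusion.** The point holds as a recommended improvement, not as an error. The text is clear on the facts: baseline is a tested timepoint in sections 11.1 and 11.2, it is not part of the primary endpoint, no covariate is named, and all five scales are available before injection.

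On the per-visit reading with 70 evaluable subjects, five-baseline adjustment changes power by about −4, +1, +9 and +18 points at r = 0, 0.3, 0.5 and 0.7. On the one-scale-over-visits reading the gain is 2 to 4 points at 35 per arm. These figures rest on 0.20 being f², on assumed correlations and, for the second reading, on an assumed 0.6 SD effect. Confidence in the size is medium because r is unknown. Removing baseline as a tested outcome and stating the response vector are worthwhile whatever r is.

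**What to change.** - Remove baseline from the tested timepoints in sections 11.1 and 11.2.
- State whether the response vector is five scales at one visit or one scale over the four post-injection visits, and restate the sample-size basis to match. On the second reading the vector falls from five responses to four.
- Prespecify baseline as a covariate in the global test: the five baseline scores in a per-visit MANCOVA, or the scale's own baseline if the vector is one scale over visits.
- Fit this model in each imputed dataset, with baseline scores in the imputation model. Name the rule for pooling the multivariate test, and report pooled adjusted differences with 95% confidence intervals.
- Label per-scale, per-visit ANCOVA estimates with own baseline (5 × 4 = 20) as supportive; they do not replace the global test.
- Describe baseline by arm without significance tests.

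**Cost.** Wording only, with no new visits or data. A five-baseline MANCOVA uses five degrees of freedom and loses up to about 4 power points at N = 70 if r is below about 0.28, or up to 2.5 points at N = 84 if r is below about 0.25. A single own-baseline covariate uses one degree of freedom and loses under 1 point at r = 0.
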